# 13.10 Early withdrawal

The following should be performed if a participant withdrawals before the end of study:

- document timepoint when withdrawal occurs and if allocated study treatment has been completed
- document reason (if known) by participant or investigator
- document if withdrawal is due to safety reasons (e.g. related to any SAE)

- if withdrawal is during study treatment, document if participant consents to continue with study follow up
- unused study drugs must be returned and destroyed
- participants have the option to continue treatment (or with a different treatment) outside of the study, at the discretion of their usual clinician
- document that data and samples collected until the point of withdrawal will be kept and used
- document if participant consents to the collection of their virological outcome (SVR12) if data is collected outside of the study (e.g. by their usual clinician, regardless of whether or not treatment is continued after withdrawal from the study)
- participant are not allowed to re-enter the study unless if no study drug is missed during the withdrawal period

# 13.11 End of trial (EOT)

The CI is delegated the responsibility of submitting the EOT notification to REC and MHRA once reviewed by sponsor. The EOT notification must be received by REC and MHRA within 90 days of the end of the trial.

If the study is ended prematurely, the Chief Investigator will notify the Sponsor, REC & MHRA including the reasons for the premature termination (within 15 days).

End of trial is defined as 3 months after the last randomised participant completes the study procedures.

# 14.0 Laboratories and samples

#### 14.1 Central Laboratories

Analyses for the main study which are standard NHS diagnostic tests will be performed at accredited local laboratories at each study site.

Central laboratories will not be required.

#### 14.2 Local Laboratories

All laboratory analyses required for this study are considered 'standard' diagnostic tests and will be performed at the NHS laboratory associated with the study site, using validated assays (i.e. Royal London Hospital, Royal Free Hospital, St George's hospital, St Mary's Hospital, Kings College Hospital). All laboratories are CPA accredited and GCP compliant.

Each laboratory will provide their accreditation documentation, methodology and reference ranges.

The list of laboratory data required pre study enrolment and tests to be performed during the study are as follows:

Haematology - haemoglobin, platelet count Biochemistry - total bilirubin, AST, albumin, creatinine, eGFR (by Cockcroft Gault or MDRD formula) Virology - HCV genotyping, HCV viral load quantification

# 14.3 Sample Collection/Labelling/Logging

Samples will be whole blood collected from participants using trained phlebotomists at each study site. For local laboratories, the local NHS health trust SOP will be followed.

These samples will NOT be anonymised and results will be accessible to authorised healthcare personnel as per standard NHS diagnostic tests.

# 14.4 Sample Receipt/Chain of Custody/Accountability

Samples processed during the study which are standard NHS diagnostic tests will follow local site SOP and the associated NHS Health Trust is accountable.

# 14.5 Sample Analysis Procedures

#### 14.5.1 The arrangements for sample analysis

For analyses which are NHS standard diagnostic tests, please refer to lab manuals.

# 14.5.2 Sample Storage Procedures

Storage of study samples will be according to NHS laboratory SOP and will be identifiable to the participant.

# 14.6 Sample and Data Recording/Reporting

Sample results will be recorded in participants' medical records, as well as in study CRF (anonymised).

# 14.7 End of study

Laboratory data will be recorded and reported in the standard way as other non-study NHS samples, and will be available for review by personnel authorised to handle confidential patient records who are outside of the study.

#### 15.0 Trial Medication

# 15.1 Name and description of investigational medicinal product(s)

This study involves the use of two medications in a fixed dose combination – Epclusa 400mg/100mg film-coated tablet, which contains 400mg sofosbuvir and 100mg velpatasvir.

Dose reduction is not permitted but discontinuation, at the discretion of the participant or investigator, is permitted. This must be documented in the participant medical notes and reported on CRF.

All subjects will initially start treatment with sofosbuvir/velpatasvir outside of the study, on the NHS treatment programme. Subjects must not have taken ribavirin along with sofosbuvir/velpatasvir. Subjects are recruited during NHS treatment period, between treatment weeks 8-12. Therefore, subjects have been dispensed with their 3rd prescription of sofosbuvir/velpatasvir (supplied as 28 tablets per bottle – i.e. one bottle every 4 weeks) by the time of study enrolment. In order to avoid wastage of high cost drugs when patients enter this study, they will continue to take the dispensed supply between weeks 8 to 12. Subjects randomised to the 12 week arm (Arm A) will receive no further drug supply. Subjects randomised to the extended treatment will receive additional study drug for weeks 13-24. (Arm B)

Study drugs (only required for weeks 13-24) will be supplied in their original manufacturer's packaging, which ensures the integrity of the product during transport and storage. Study drugs will be labelled at the site trial pharmacy (or delegate) with approved clinical trial labels in accordance with Annex 13. It should contain:

- participant's study details
- dosing instructions
- contact details for study investigator
- the phrase 'keep out of reach of children'
- the phrase 'for clinical trial use only'
- trial reference code (EudraCT number)

The original manufacturer's Patient Information Leaflet will be provided.

Each dispensing episode will be for a 4 week supply. Patients are to return the IMP container before the next 4 weeks is dispensed.

# 15.2 Legal status of the drug

Sofosbuvir/velpatasvir is licensed in the EU for use in patients with all genotypes of chronic HCV, including patients with decompensated cirrhosis, co-infection with HIV and those with post-liver transplant HCV recurrence. Thus sofosbuvir/velpatasvir is approved for use in the study target population. The license recommends for most patients sofosbuvir/velpatasvir should be used for 12 weeks. For patients who are harder to treat, namely genotype 3 HCV infected patients with compensated cirrhosis, addition of ribavirin can be considered, and for patients with decompensated cirrhosis, ribavirin should be added.

Ribavirin is associated with significant adverse events, and it is therefore advantageous to offer ribavirin-free treatments for patients who are least able to tolerate it. This trial uses 24 weeks of sofosbuvir/velpatasvir, as the test treatment, to compare with the standard of care for 12 weeks.

The 24 week duration has been evaluated in a Phase III trial showing no increased adverse events compared to the 12 week duration, unlike the combination with ribavirin [16]. The 24 week regime has not been recommended according to the drug license as the longer duration was not associated with significantly improved efficacy; however the study was not powered to detect significant differences in SVR between treatment groups and only 12 patients received the 24 week duration. The use of sofosbuvir/velpatasvir with ribavirin for 24 weeks can, according to license, be considered for patients who previously failed therapy on an NS5A containing regime. International guidance from EASL in 2016 recommends patients with genotype 3 HCV infection who have contraindications to the use of ribavirin, or poor tolerance to ribavirin on treatment should receive sofosbuvir/velpatasvir for 24 weeks without ribavirin [23].

Given the lack of clear evidence guiding the use of treatments in subpopulations of HCV patients, NHS England provides treatments which are off-label but supported by robust data. NHS England has indicated that if this study provides evidence supporting the use of 24 weeks of sofosbuvir/velpatasvir, the regime will become adopted into the treatment portfolio.

Response-guided duration of treatment is not routinely used for DAA therapies therefore the MHRA has deemed the above study treatments as IMPs when used for either durations, since the current practice does not involve the use of on-treatment viral load to determine the duration of treatment required.

This study is being carried out under a Clinical Trial Authorisation (CTA).

The study excludes participants with renal failure (defined as eGFR <30ml/hr or dialysis dependent) as the treatment drugs are not licensed for this population.

# 15.3 Summary of Product Characteristics (SmPC) or IB

Please see Summary of Product Characteristics for sofosbuvir/velpatasvir (Epclusa).

#### 15.4 Drug storage and supply

All participants in this study are initially treated with sofosbuvir/velpatasvir for at least 8 weeks as standard NHS treatment. Drug supply is registered on Blueteq which allows monitoring of high cost drugs by NHS England. Prescriptions and dispensing will take place every 4 weeks.

Upon enrolment into the study, from week 8 to 12, sofosbuvir/velpatasvir will be considered standard therapy. In order to avoid wastage of high cost drugs, patients will complete the medication which is NHS-dispensed, but the next due prescription will be supplied as IMP. Therefore, subjects in the 12 week arm (Arm A) will not receive further study drug after completing their dispensed NHS prescription for week 8 to 12. Subjects in the extended treatment arm (Arm B) will have further study drug dispensed for week 13 to 24. The extended treatment must be registered on BlueTeq.

The study drugs will be supplied in their original packaging but labelled with trial medication labelling. Storage and supply will be in accordance to the Trial Pharmacy SOP (or that of contracted delegate).

# 15.5 Supplier

The IMPs will be sourced from commercial stock by the site and will be delivered to the study sites according to their contracts with the NHS Trust. Study drug will be purchased by the NHS Trust of the study site and reimbursed by NHS England.

See IMP Manual for details of local drug supply and IMP management plan for detail of trial-wide supply procedures.

#### 15.6 Manufacturer

Sofosbuvir/velpatasvir (Epclusa 400mg/100mg) is manufactured by Gilead Sciences Ltd.

# 15.7 How the drug should be stored

The IMPs requires no special storage conditions (below 25 degrees Celsius)., NHS Trust and study site clinical trial pharmacy guidelines. Records of storage will be maintained by the delegated site pharmacy and any excursions from the storage instructions will be documented, and reported to the PI, CI and Sponsor.

Instructions for storage once dispensed from pharmacy is as per Patient Information Leaflet which is included with the study IMP packaging. The manufacturers advise no special storage conditions are required.

# 15.8 Details of accountability

The study site pharmacy is responsible for dispensing in line with local procedures to ensure the integrity of the drugs. All NHS Trust pharmacies will adhere to their local policy on accountability of drugs.

The batch or lot number and expiry date of dispensed drugs should be recorded.

Investigators will perform pill count and review returned empty bottles during on-treatment study visits. Missed pills will be recorded in the CRF. Investigators will retrospectively document any missed pills in the period between treatment start to enrolment.

# 15.9 Medication destruction/return and Recall

IMP which is not used by a participant or is found to have breached its conditions for use should be returned to pharmacy and destroyed according to local guidelines. Returned and destroyed IMP must be documented.

# 15.10 Prescription of IMP / Placebo/NIMP

Participants will initially start treatment on the NHS programme, and will be prescribed according to local procedures, checked and signed by authorised personnel. Treatment will be logged on BlueTeq. Upon entering the study, prescriptions of study drug must be signed by study investigators authorised by the delegation log.

The Trial Pharmacy will be provided with a delegation log detailing which investigators are authorised to sign prescriptions.

# 15.11 Preparation and labelling of IMP

The drugs sofosbuvir/velpatasvir is a fixed dose combination tablet which does not need any preparation.

### 15.12 Preparation and Administration of IMP

Sofosbuvir/velpatasvir should be taken orally, swallowed whole, with or without food. Due to its bitter taste, the film-coated tablet should not be chewed or crushed. It should preferably be taken at the same time each day.

Missed doses should be managed according to drug SmPC instructions. If sofosbuvir/velpatasvir is missed, another tablet should be taken within 18 hours of the missed dose, and the next due dose taken at the usual time. If the missed dose is more than 18 hours, then the missed dose should be omitted and the next due dose taken at the usual time.

If the subject has vomiting within 3 hours of taking sofosbuvir/velpatasvir, they should take another tablet. If vomiting occurs after 3 hours of the dose, they should take the next due dose at the usual time.

If the subject accidentally takes more than the recommended dose, they should contact the study team before taking the next due dose.

Adherence to dosing will be monitored during study visits.

# 15.13 Dosage schedules

Sofosbuvir/velpatasvir should be taken as one tablet per day, preferably at the same time daily, for total 12 or 24 weeks.

#### 15.14 Dispensing of IMP

Dispensing will be according to guidelines in place within the Trust and Clinical Trial Pharmacy, who are responsible for dispensing in line with their local dispensing procedures and excursion management normal practices.

Drugs dispensed as NHS treatment but used after a participant has enrolled (a period of no more than 4 weeks) will be recorded only in the NHS pharmacy. Drugs dispensed as IMP by the Trial Pharmacy must be logged to allow tracking of study drugs. All trial pharmacists must have documented training for this trial.

A dispensing label with study specific information will be applied, the Batch and expiry number must not be obscured.

#### 15.15 Dosage modifications

Dose modification of sofosbuvir/velpatasvir is not permitted. There are no stopping rules based on virological outcome but discontinuation may occur at the discretion of investigator or at participant request to withdraw. Participants who do not achieve end of treatment virological response are not permitted to extend treatment within this study.

# 15.16 Known drug reactions and interaction with other therapies

Refer to clinical particulars within SmPC for contraindications, special warnings, interaction with other medicinal products, and other undesirable effects.

Velpatasvir is an inhibitor of drug transporter P-glycoprotein, breast cancer resistance protein (BCRP), organic anion-transporting polypeptide (OATP) 1B1 and OATP1B3. Co-administration with medicinal products which are substrates of these transporters may increase the exposure of such medicinal products.

Sofosbuvir and velpatasvir are substrates of drug transporters P-gp and BCRP. Velpatasvir is also a substrate of drug transporter OATP1B. *In vitro*, slow metabolic turnover of velpatasvir by CYP2B6, CYP2C8 and CYP3A4 was observed. Medicinal products that are potent inducers of P-gp or potent inducers of CYP2B6, CYP2C8, or CYP3A4 (e.g. rifampicin, rifabutin, St. John's wort, carbamazepine, phenobarbital and phenytoin) may decrease plasma concentrations of sofosbuvir or velpatasvir leading to reduced therapeutic effect of sofosbuvir/velpatasvir. The use of such medicinal products with Epclusa is contraindicated. Medicinal products that are moderate P-gp inducers or moderate CYP inducers (e.g. oxcarbazepine, modafinil or efavirenz) may decrease sofosbuvir or velpatasvir plasma concentration leading to reduced therapeutic effect of Epclusa. Co-administration with such medicinal products is not recommended with Epclusa. Co-administration with medicinal products that inhibit P-gp or BCRP may increase sofosbuvir or velpatasvir plasma concentrations. Medicinal products that inhibit OATP, CYP2B6, CYP2C8, or CYP3A4 may increase plasma concentration of velpatasvir. Clinically significant medicinal product interactions with Epclusa mediated by P-gp, BCRP, OATP, or CYP450 inhibitors are not expected; Epclusa may be co-administered with P-gp, BCRP, OATP and CYP inhibitors.

#### 15.17 Prior and Concomitant medication

To avoid drug-drug interactions, the following list of concomitant medications are not permitted, according to product SmPCs. Participants taking these medications must have discontinued prior to starting sofosbuvir/velpatasvir (this is expected to be in line with standard care practice).

In accordance with the SmPC of Epclusa (sofosbuvir/velpatasvir) concomitant use of the following medications are contraindicated:

Anticonvulsants - carbamazepine, phenytoin, phenobarbital, oxcarbazepine Antimycobacterials – rifampicin, rifabutin, rifapentine

Antiretrovirals - efavirenz

St John's wort

Modafinil

Proton-pump inhibitors should be avoided and if necessary, sofosbuvir/velpatasvir should be taken with food and administered 4 hours before proton pump inhibitor, at maximum doses equivalent to 20mg omeprazole per day.

Amiodarone should be avoided and if necessary, close monitoring is required

The following medications should be co-administered with caution:

Digoxin

Amiodarone

Rosuvastatin (do not exceed 10mg), other statins consider dose reduction Antacids (e.g. aluminium hydroxide) – separate administration by 4 hours

H2 antagonists — administer simultaneously or staggered from sofosbuvir/velpatasvir, at a dose not exceeding the equivalent of 40mg famotidine twice daily

Dabigatran

Tenofovir

For management of other concomitant medications, refer to SmPC, EASL practice guidelines and http://hep-druginteractions.org/

#### 15.18 Trial restrictions

No dietary restrictions are required for the trial. Concurrent alcohol or recreational drug use is not an exclusion for this trial, but the subject's suitability to enrol or continue within the study will be at the discretion of investigators.

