### 11.6 Trial Design

This is an open-label, parallel design study of 12 and 24 weeks of sofosbuvir/velpatasvir. Subjects are initially started on NHS standard of care treatment, and are consented to participate between treatment week 8-12 (of the standard 12 week course). This design is chosen for several reasons:

- To maximise the time between fulfilling entry criteria (i.e. week 2 ≥ 30iu/mL) and consent, to allow subjects time to consider participation
- Given sofosbuvir/velpatasvir is generally well tolerated, early discontinuation is usually due to non-adherence. By recruiting patients after at least 8 weeks, the study is more likely to recruit subjects willing to adhere to extended treatment. The study specifies that subjects have taken at least 90% of prescribed drugs by screening
- Sofosbuvir/velpatasvir is an expensive treatment and in order to prevent wastage of prescribed NHS treatment when subjects commence on the trial, they are recruited only after the final prescription (each prescription is for one bottle of sofosbuvir/velpatasvir which contains 4 weeks of drug) has been dispensed at treatment week 8. Therefore, only subjects randomised to extended treatment will be dispensed with study drugs.

Maximum duration of participation is 16 weeks for Arm A (12 weeks treatment) - 4 weeks of observation during standard of care treatment, 12 weeks of follow-up, and 28 weeks for Arm B (24 week treatment arm) – 16 weeks of study treatment (4 weeks of standard of care treatment plus 12 weeks of additional IMP treatment), 12 weeks of follow-up.

Treatment week 0 is defined as commencement of sofosbuvir/velpatasvir on NHS treatment programme, before enrolment into the study. Subjects can be pre-screened for study eligibility once week 2 virological response becomes available. Patient information sheet can be provided to interested subjects, but they cannot be consented to participate until week 8 of treatment. Screening and randomisation can take place until the end of standard treatment at week 12.

Upon enrolment into the study until treatment week 12, subjects will proceed according to protocol but they will complete drugs prescribed as part of NHS treatment prior to enrolment. This is in order to reduce wastage of high cost drugs. Sites must ensure sufficient time between enrolment and end of 12 weeks treatment, to dispense additional IMP for participants randomised to arm B (24 weeks).

Study visits are as follows:

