#### 13.9 Withdrawal criteria

Participants have the right to withdraw consent for study participation at any time. Participants will be informed before enrolment that if they wish to withdraw from the study, or if they are withdrawn for any reasons (such as those listed below), study treatments will be discontinued and no further study procedures or visits will be performed. However, participants will be asked at enrolment to consent to having their treatment virological outcome (SVR at 12 weeks after treatment discontinuation) collected, if available. Participants can opt to withdraw this consent, and withdraw

completely from the study; at this point no further data will be collected. Data obtained up to the point of withdrawal will be kept.

When a participant is withdrawn from the study, this is recorded in the medical notes, along with his or her consent (or withdrawal of consent) for collection of treatment virological outcome data.

Participants who withdraw from the study will be notified that they will discontinue treatment with study drugs, and unused study drugs must be returned. They have the option to continue treatment with sofosbuvir/velpatasvir (or other HCV treatment regimes) as routine NHS standard of care at the discretion of their usual clinician. If a participant withdraws during treatment week 8-12, while taking the NHS-supplied sofosbuvir/velpatasvir, the drugs should be returned according to the local NHS pharmacy policy and they may continue to use the drugs on the advice of their usual clinician.

Participants who experience intolerable toxicity or for other clinical reasons according to the investigator can discontinue the study drugs. Dose reduction of sofosbuvir/velpatasvir is not permitted. Participants who discontinue treatment can remain on the study (for follow up) provided they do not withdraw consent.

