# 15.19 Assessment of compliance

Compliance will be monitored via pill counting and checking returned empty bottles during study visits. Missed pills will be documented in CRF. Investigators will reiterate dosing schedule and the importance of compliance for efficacy. Participants are considered lost to follow up if there is no end of study visit at post treatment week 12+4 weeks.

There is no provision for supplying additional IMPs which are lost or damaged during the trial. Participants should continue on the study but doses missed due to insufficient drug supply should be recorded as missed doses. Investigators can dispense the next due prescription early to cover for lost or damaged medication. According to local pharmacy policy, if surplus/ replacement medication is available (for example if another patient withdraws from treatment), this can be supplied as IMP for a study participant, provided the medication has not been dispensed from pharmacy, and the usual storage and packaging requirements are complied with.

Any study IMP which is dispensed and unused by the participant will be recalled and destroyed in the site pharmacy. For participants who withdraw during study treatment, they may be eligible to continue treatment on the NHS programme according to their usual clinician's judgement and local Trust guidelines.

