# 19.11 Procedure(s) to account for missing or spurious data

To reduce missing data on the primary outcome, SVR12 will be defined as HCV RNA <15iu/mL from 12 to 16 weeks after end of treatment. This widens the window when SVR12 can be reported. A negative HCV RNA at any point after 12 weeks post-treatment is clinically considered to be a sustained virological cure. Negative HCV RNA at less than 12 weeks post-treatment will be considered non-SVR12.

Non SVR12 will be differentiated by true viral relapse or missing data due to lost to follow up, to allow per-protocol analysis.

Given data is time point specific, data outside of the defined window cannot be carried forward to replace missing data.

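### Section 15.18 lets unblinded investigators end study participation, not only study drug, for alcohol or drug use, which conflicts with 13.9 and puts the SVR12 result at avoidable risk

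*Protocol*

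**What the plan says.** Section 15.18 states that concurrent alcohol or recreational drug use is not an exclusion, but that the participant's "suitability to enrol or continue within the study will be at the discretion of investigators". The discretion covers the study as a whole, and it applies after enrolment as well as before.

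Section 11.6 describes the trial: "This is an open-label, parallel design study of 12 and 24 weeks of sofosbuvir/velpatasvir". Investigators therefore know the arm.

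Section 13.9 gives the consequence for participants who withdraw or are withdrawn, whatever the reason: "study treatments will be discontinued and no further study procedures or visits will be performed". It adds a retrieval route: "participants will be asked at enrolment to consent to having their treatment virological outcome (SVR at 12 weeks after treatment discontinuation) collected, if available". Section 13.10 repeats it at the point of withdrawal: "document if participant consents to the collection of their virological outcome (SVR12) if data is collected outside of the study". Section 13.8.4 names the usual clinician as the source.

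For toxicity or other clinical reasons, 13.9 takes a different line: "Participants who discontinue treatment can remain on the study", provided consent stands. Section 17.11 likewise allows follow-up for the primary outcome when treatment stops because of pregnancy.

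On the endpoint, 15.19 says "Participants are considered lost to follow up if there is no end of study visit at post treatment week 12+4 weeks", and 19.11 says "Non SVR12 will be differentiated by true viral relapse or missing data due to lost to follow up". A missing SVR12 is therefore one kind of non-SVR12.

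**The concern.** Discretion over who enrols is ordinary. Section 15.18 carries it past randomisation, with no criterion, in a trial where the person deciding knows the arm. Section 12.2 already excludes use judged likely to interfere with the trial, so the participants affected are those knowingly enrolled despite some use.

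The rest of the protocol separates stopping drug from leaving follow-up; 15.18 does not. In Arm A after week 12 no drug is being given, so ending participation there only forgoes visits and the SVR12 sample.

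At stake is the primary endpoint. Section 9.3 defends the open-label design on the ground that the laboratory does not know the allocation. That does not protect a decision about whether the sample is taken at all. Arm B is exposed to that decision for longer, so outcomes lost in this way would tend to fall more on the 24-week arm. Individual judgements could also move the contrast either way.

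**Working it through.** **1. The plan's own figure.** Section 19.1 gives 65% against 95% SVR12, 80% power, 95% confidence and 24 per arm. With unpooled variance and two-sided 0.05:

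n = (1.960 + 0.842)² × (0.65×0.35 + 0.95×0.05) / 0.30² = 23.98, so 24 per arm. This reproduces.

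Exact power of the uncorrected chi-square test is 80.8% at 24 per arm and 88.0% at the 30 per arm to be recruited.

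**2. Time at risk, from randomisation to the SVR12 visit** (sections 11.6 and 13.8.2; final visit at week 24 in Arm A and week 36 in Arm B):

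- Randomised at week 8: 16 and 28 weeks, ratio 1.75. These are the stated maxima.
- Randomised at week 12: 12 and 24 weeks, ratio 2.0.
- Counting Arm B only from week 12, when the first extension dose is due: 24/16 = 1.5 up to 24/12 = 2.0.

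The third line matters because 19.5 keeps an Arm B participant in the analysis only after at least one extension dose. Removal before that dose takes the participant out of the analysis set and does not count as a failure. Arm A has no matching rule.

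**3. Illustration of size.** The documents give neither a removal rate nor a retrieval share, so both are assumed. Let w be the fraction of Arm A removed, r the exposure ratio and s the share of SVR12 results retrieved in window. Assume a constant weekly rate and removal that is unrelated to cure and does not change it.

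- Arm B removed = 1 − (1 − w)^r
- Observed SVR12 = planned rate × (1 − removed × (1 − s))

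Example with w = 2%, r = 1.75, s = 0: Arm B removed = 1 − 0.98^1.75 = 3.5%. Arm A = 0.65 × 0.98 = 63.7%; Arm B = 0.95 × 0.965 = 91.7%. The difference is 28.0 points and exact power is 77%.

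Exact power at 30 per arm, for r from 1.75 to 1.5:

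| Arm A removed | Arm B removed | None retrieved | Half retrieved | 80% retrieved |
|---|---|---|---|---|
| 0% | 0% | 88% | – | – |
| 2% | 3.5% to 3.0% | 77–79% | 83–84% | 86% |
| 5% | 8.6% to 7.4% | 62–67% | 75–77% | 83–84% |

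At r = 2.0 with none retrieved, power is 75% in the 2% case and 57% in the 5% case.

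The table keeps 30 per arm throughout. It does not model the small loss of Arm B numbers from removals before the first extension dose.

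**4. Bias when the arms are truly equal.** With 90% cure in both arms (assumed), the 5% case at r = 1.75 and none retrieved gives 0.90 × (0.05 − 0.086) = −3.2 points against 24 weeks. One participant in an arm of 30 is 1/30 = 3.3 points.

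**The case against.** Section 15.18 is one sentence in the medication chapter, and its main message is permissive. Withdrawal is governed by 13.9, which does not list alcohol or drug use as a ground and, for investigator-led stopping on clinical grounds, keeps the participant in follow-up. Section 15.15 also frames discretion as discontinuing drug. On that reading, 15.18 was never meant as a separate power to end follow-up. This shows that the sections need reconciling, but it does not change what 15.18 says.

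A reader might infer that every removal turns a cure into a failure. The documents do not support that. Consent to collect SVR12 is sought at enrolment and recorded again at withdrawal, and HCV RNA is a routine test in site NHS laboratories. The loss is possible, not automatic. One gap remains: 19.11 does not say that a usual-care result counts, while 15.19 labels anyone without the end-of-study visit as lost to follow-up.

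A reader might also take the 62% power figure as the expected effect. It assumes zero retrieval and about 4 of 60 participants removed on these grounds (30 × 0.05 + 30 × 0.086 = 4.1). Section 19.2 does not expect withdrawal to be a major problem, and entry requires 90% adherence. The planned power is 80%, with 60 recruited to allow for withdrawals, so 88% is the power with no attrition at all. These points stand. The allowance replaces lost numbers, however; it does not remove bias when an unmeasured cure is scored as a failure.

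**Conclusion.** The point holds as a conflict between sections with a route to the primary endpoint. As written, 15.18 lets an unblinded investigator end a randomised participant's place in the study, and 13.9 then ends the visits. SVR12 rests on consent and on an in-window usual-care result, failing which the participant is non-SVR12. Comparable cases in 13.9 and 17.11 keep follow-up.

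Arm B's time at risk is 1.75 times Arm A's at the stated maxima, within a range of 1.5 to 2.0. A flat statement that it is twice as long would hold only for randomisation at week 12. Arm B removals before the first extension dose act differently, by exclusion from the analysis set.

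The size cannot be established from the documents. With 80% of results retrieved, power stays at 83% or above in both illustrated cases for ratios of 1.5 to 1.75. It falls below 80% in the 2% case only when retrieval is poor, and in the 5% case even with half retrieved. All of this assumes a constant removal rate and no link between removal and cure. Severity is minor to moderate.

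**What to change.** Reconcile 15.18 with 13.9 by stating in both that a randomised participant is not removed from follow-up by investigator decision because of alcohol or recreational drug use, and that scheduled visits and the SVR12 sample continue unless the participant withdraws consent. Changing 15.18 alone would leave the general withdrawal wording in 13.9 open.

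In 19.11, state that an SVR12 result from usual care within the 12 to 16 week window counts towards the primary endpoint, and align the definition of loss to follow-up in 15.19 with that.

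Leave any decision about study drug as the protocol has it. The cost is a few sentences and a small number of retained visits that are already scheduled.
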